6.2 Sample Size and Power

No formal sample size calculations have been performed. The number of subjects participating in each cohort is common in early clinical pharmacology studies and is considered sufficient to achieve the objectives of the study.

6.3 Randomization

A randomization list for each part will be produced by Vertex Biostatistics or a qualified randomization vendor. The Vertex study biostatistician will review and approve the dummy randomization list. The final randomization list will be reviewed and approved by a designated unblinded biostatistician who is not a member of the study execution team (SET).

Only subjects who have completed screening assessments and are eligible for participation in the study will be randomized to receive active study drug or placebo. Randomized subjects will be assigned a unique subject number. A list identifying subjects by their subject number will be maintained in the study file at the CRU.

6.4 Replacement

Subjects who withdraw or are withdrawn before the first dose of study drug on Day 1 for each part may be replaced.

Subjects who withdraw or are withdrawn for non-safety reasons during the study drug treatment periods may be replaced at Vertex's discretion.

6.5 Blinding and Unblinding

This will be a double-blind study with the exception of Cohort A7, which will be open-label.

6.5.1 Blinding

Blinding of subject treatment assignments will be maintained until database lock. The packaging and labeling of study drug will be done to ensure that treatment assignments are blinded within each cohort in all parts of the study.

During the conduct of the study, all study personnel will be blinded to subject treatment assignments except for

- the unblinded site monitor;
- Bioanalytical CRO analyzing PK samples and Vertex Bioanalytical personnel who is not a member of the SET but reviews raw data from Bioanalytical CRO. The Vertex Bioanalytical SET member will continue to be blinded;
- vendor preparing the unblinded statistical and PK/PD analysis of continuous ECG data collected in Part A (with the exception of Cohort A7);
- the unblinded biostatistician preparing the randomization list as well as an unblinded quality control (QC) biostatistician;
- the dispensing contracted pharmacist;
- the pharmacy QC/quality assurance personnel, as applicable; and
- Vertex GPS and Regulatory Affairs, when required to satisfy regulatory reporting requirements.

The Vertex medical monitor may, for matters relating to safety concerns, unblind individual subjects at any time.

A limited Vertex team, which may include members of the Vertex SET, may be unblinded to individual subject treatment assignments for the purposes of review of PD, PK/PD, and/or safety data. No unblinded data or results of unblinded analyses will be shared with the clinical research unit or with blinded Vertex personnel. All instances of unblinding by Vertex personnel will be documented.

Bioanalytical results (i.e., concentrations of VX-445) will be reported by the bioanalytical CRO using masked identification numbers for PK analysis.

6.5.2 Unblinding

At the initiation of the study, the study site will be instructed on the method for breaking the blind. The unblinding method will be either a manual or electronic process.

Unblinding of Individual Subject Treatment Assignments by Investigator for Medical Emergencies or Urgent Clinical Situations

Unblinding of the individual subject's treatment by the investigator will be limited to medical emergencies or urgent clinical situations in which knowledge of the subject's study treatment is necessary for clinical management. In such cases, investigators will use their best judgment as to whether to unblind without first attempting to contact the medical monitor to discuss and agree to the need for unblinding. If investigators deem it not necessary to unblind immediately, they will first attempt to contact the medical monitor to discuss and agree to the need for unblinding. If investigators have tried but are unable to reach the medical monitor, they will use their best judgment, based on the nature and urgency of the clinical situation, and may proceed with unblinding without having successfully reached and discussed the situation with the medical monitor. In case of emergency, the investigator will have the final decision and unilateral right for unblinding.

Contact information for the medical monitor (or appropriate backup) will be provided in a separate document.

In addition, the Vertex Medical Information Call Center ([REDACTED]) will answer calls 24 hours a day, 7 days a week, 365 days of the year, and will triage these calls to the study medical monitor or appropriate backup.

If a subject's treatment assignment has been unblinded for a medical emergency or urgent clinical situation, the medical monitor will be notified within 24 hours of the unblinding event. The reason and the date of the unblinding will be documented clearly in the subject's study file. Information about the treatment assignment obtained from the unblinding will be maintained in a secure location with controlled access and will not be shared with the sponsor (Vertex), CRO, or any site personnel (other than the physician treating the subject). In addition, the investigator will consider whether the clinical event that prompted unblinding will be considered a serious adverse event (SAE), according to the regulatory definitions or criteria for SAEs, and if so, submit an SAE report to GPS or designee, per Section 13.1.2 of the protocol.

Unblinding of Individual Subject Treatment Assignments by Vertex GPS or Designee for SAEs or Safety Concerns

Vertex GPS or designee will also unblind any SAE reports in compliance with regulatory reporting requirements. In addition, Vertex may, for matters relating to safety concerns, unblind individual subjects at any time.

Unblinding: Interim Analysis Results

When an IA is performed after all subjects in Part C have completed the Safety Follow-up Visit, results from Parts A, B, and C will be unblinded for full review by the Vertex study team.

8 ANALYSIS SETS

8.1 All Subjects Set

The All Subjects Set is defined as all subjects who were randomized or received at least 1 dose of study drug. The All Subjects Set will be used for individual subject data listings, and the disposition summary table, unless specified otherwise.

8.2 Safety Set

The Safety Set will include all subjects who received at least 1 dose of study drug. All safety, demographics, baseline characteristics, study drug exposure, and concomitant medications will be summarized for the Safety Set.

9 STATISTICAL ANALYSIS

9.1 General Considerations

The Schedule of Assessments is provided in [Appendix A](#).

The precision standards for reporting safety variables are provided in an internal Biometrics document that specifies the programming rules including the precision for derived variables.

Continuous data will be summarized using the following descriptive summary statistics: the number of subjects (n), mean, standard deviation (SD), standard error (SE), median, minimum value (min), and maximum value (max). Unless otherwise specified, minimum and maximum

values will be reported with the same precision as the units of the raw data. The mean, median, SD, and SE will be reported to 1 additional decimal place. Any values that require a transformation to standard units (metric or International System [SI]) will be converted with the appropriate precision.

Categorical data will be summarized using frequency counts and percentages. Percentages will be presented to 1 decimal place.

Treatment Emergent (TE) Periods:

For subjects included in all cohorts in Parts A (except Cohort A7), B and C, One single TE period will begin from the initial administration of study drug through the Safety Follow-up Visit.

Treatment Groups

The Treatment Groups in Part A (excluding Cohort A7), Parts B and C will be defined as the corresponding dose groups.

For subjects participating in Cohort A7 in Part A, 3 TE periods will be analyzed:

- **TE Period 1 (tablet [fasted])** will begin from the initial administration of study drug on Day 1 until the administration of study drug on Day 7.
- **TE Period 2 (tablet [fed])** will begin from the initial administration of study drug on Day 7 until the administration of study drug on Day 13.
- **TE Period 3 (IV [fed])** will begin from the initial administration of study drug on Day 13 through the Safety Follow-up Visit.
- The 3 **Treatment Groups** in Cohort A7 will correspond to tablet [fasted], tablet [fed] and IV [fed] respectively.

Baseline value:

The baseline value will be defined as the most recent non-missing measurement (scheduled or unscheduled) collected before the first administration of study drug on Day 1. If a pre-dose measurement is missing and no drug-free unscheduled assessments are performed before the first dose of the study, the baseline will be missing. For ECG, baseline will be defined as the most recent non-missing measurement (or the average of triplicate measurements, if the most recent non-missing measurement is obtained in triplicate), before the first dose of study drug on Day 1 of the Treatment Period.

For Cohort A7

The baseline value will be defined as the most recent non-missing measurement collected before the initial administration of study drug on Day 1. If the pre-dose measurement is missing and no drug-free unscheduled assessments are performed before the first dose of study drug, the baseline value will be determined to be missing.

Change from baseline value will be defined as change from baseline at each scheduled post-baseline time point. The change from baseline value will be calculated as the post-baseline value minus the baseline value.

Visit Window: As the majority of assessments are predicted to be on schedule, visit windows will not add significant value to the analysis and will not be applied.

Unscheduled visits: Subject data obtained during unscheduled visits will not be summarized but will be included in subject data listings only, except for the ECG analysis of the maximum values during TE period and maximum changes from baseline in QT/QTcF intervals during TE period (see Protocol Section 11.7.5). Unscheduled visit values will not be used to impute missing scheduled visit values, except for baseline calculation.

Incomplete/missing data (e.g., dates, post-baseline values) will not be imputed, unless otherwise specified; i.e., all missing values and missing post-baseline values will remain as missing in all statistical analyses and listings, unless otherwise specified.

Outliers: No formal statistical analyses will be performed to detect and/or remedy the presence of statistical outliers.

Hypothesis testing: No statistical hypothesis testing will be performed.

All subject level data, including those derived, will be presented in the individual subject data listings; listings will be based on the All Subjects Set.

Unless otherwise specified, the analyses will be done by Treatment Group in all cohorts for Parts A, B and C. Separate summary tables will be produced for each part.

- Part A (Cohorts A1 through A5): Placebo, VX-445 20 mg, VX-445 60 mg, VX-445 120 mg, VX-445 240 mg, VX-445 360 mg, and VX-445 Total. The dose levels are subject to change to reflect the real dose levels.

- Part A (Cohort A7): tablet [fasted] 100 mg, tablet [fed] 100 mg and IV [fed] 20 mg.

- Part B: Placebo, VX-445 60 mg QD, VX-445 120 mg QD, VX-445 240 mg QD, VX-445 340 mg QD and VX-445 Total.

- Part C: Triple Placebo, VX-445 200 mg QD + TEZ/IVA, VX-445 280 mg QD + TEZ/IVA, VX-445 100 mg QD + TEZ/IVA and VX-445 + TEZ/IVA Total.

9.2 Background Characteristics

9.2.1 Subject Disposition

Disposition summary will be based on the All Subjects Set.

The number and percentage of subjects in each disposition category (randomized; included in the Safety Set; PD set; completed dosing; completed study; discontinued treatment for Cohort A7 and for all cohorts in Parts B and C, and discontinued study with a breakdown of the reasons for early discontinuation, when applicable) will be summarized overall and by Treatment Group for Parts A (Cohorts A1 through A6), B and C, and by treatment sequence for Cohort A7.

9.2.2 Demographics and Baseline Characteristics

Demographics, medical history and baseline characteristics summary will be based on the Safety Set.

Demographics and baseline characteristics (age, sex, race, ethnicity, weight, height, BMI, medical history, baseline spirometry [Parts B and C] [REDACTED] will

be summarized overall and by Treatment Group for Parts A (Cohorts A1 through A6), B and C, and by sequence for Cohort A7.

No statistical tests will be done to evaluate baseline imbalances between groups.

9.2.3 Prior and Concomitant Medications

Medications will be coded using the World Health Organization-Drug Dictionary Enhanced (WHO-DDE) 1st March 2016, Format B2 or higher. Medications used in the study will be categorized as prior and/or concomitant medications as follows:

1. **Prior medication:** Medication that started before the first dose of study drug, regardless of when dosing of the medication ended
2. **Concomitant medication:** Medication received at or after the first dose of study drug, medication that was received before initial dosing and continued after initial dosing of study drug, or medication with missing stop date

If a medication start date is on or after the date of initial dosing of the study drug, then the medication will be summarized as concomitant medication regardless of whether the medication end date is missing or not. If a medication end date is before the date of initial dosing of the study drug, then the medication will be summarized as prior medication regardless of whether the medication start date is missing or not. Note that medication that started before initial dosing of the study drug and continued after initial dosing will be summarized as prior medication and separately as concomitant medication.

Missing or partial dates will be imputed for medication. Algorithm for missing or partial start date is:

Missing day: first day of the month is imputed;
Missing month: January is imputed;
Missing year: not imputed.

Algorithm for missing or partial end date is:

Missing day: last day of the month is imputed;
Missing month: December is imputed (31 December if day is also missing);
Missing year: not imputed.

Missing data algorithms will be reviewed to ensure the algorithm works. For example, end date will not be before the start date after the imputation.

For Cohort A7, concomitant medications will be assigned to each TE period based on the start date of the medication and the study drug administration dates (concomitant medications taken during the TE period will be assigned to the TE period, and so forth).

Note that a concomitant medication may be assigned to multiple TE periods.

Prior medications will not be summarized, but will only be listed. Concomitant medications will be summarized using preferred name by Treatment Group and overall for all cohorts in Parts A (except for Cohort A7), B and C, and by Treatment Group only for Cohort A7. Concomitant Medications summary will be based on the Safety Set.

9.2.4 Study Drug Exposure and Compliance

Study drug exposure (i.e., duration of treatment) will be summarized by Treatment Group and overall for all cohorts in Parts B and C for the Safety Set.

Study drug exposure (in days) will be defined as (last date of dosing – first date of dosing) + 1.

The study drug administration will be presented in an individual subject listing for Parts A, B and C.

9.3 Safety Analysis

Safety is the primary objective of this study. The overall safety profile of VX-445 will be assessed in terms of the following primary (safety) endpoints:

- Incidence of treatment-emergent adverse events (TEAEs)
- Clinical laboratory values (including coagulation studies)
- ECG outcomes
- Vital signs
- Spirometry (Parts B and C only)

Safety analyses will be performed by Treatment Group and overall for all cohorts in Parts A (except for cohort A7), B and C, and by Treatment Group only for Cohort A7. Safety analysis will be conducted for the Safety Set. Safety data will be presented in the individual subject data listings based on the All Subjects Set. Only descriptive analysis of safety will be performed (i.e., no statistical hypothesis testing will be performed).

[Table 9-1](#) shows the safety summaries (e.g., raw value, change from baseline, incidence, and clinical abnormalities) that will be summarized for TEAEs, clinical laboratory values, 12-lead ECG, vital signs, spirometry (Parts B and C), and physical examination. Details are provided in the corresponding subsections.

The incidence of TEAEs will be summarized. TEAE summaries will include the following: all TEAEs (regardless of severity or relationship to study drug), serious adverse events (SAEs), TEAE severity, TEAE relationship, and discontinuations of study drug treatment due to TEAEs.

For the non-AE safety evaluations (clinical laboratory, spirometry, ECGs and vital signs), raw values, and changes from baseline will be summarized as indicated in [Table 9-1](#). For example, an “X” under the raw value column (second column) means that the raw values for the safety evaluation will be summarized; an “X” under the Change column (third column) means that change will be summarized.

Throughout this section, “change” refers to absolute change from baseline.

Table 9-1 Summaries Planned for Safety Data

Safety Assessment	Incidence	Raw Value	Change	Clinical Abnormalities
TEAEs	X			Not applicable
Hematology and chemistry		X	X	Present in listing only
Coagulation		Present in listing only		Present in listing only
Urinalysis		Present in listing only		Present in listing only
12-lead ECG		X	X	Present in listing only
Vital signs		X	X	Not applicable
Spirometry (Parts B and C)		X	X	Not applicable
Physical Examination		Present in listing only		Not applicable

ECG: electrocardiogram; TEAEs: treatment-emergent adverse events; X: safety assessment will be summarized in tables.

9.3.1 Adverse Events

AEs will be coded according to MedDRA (Version 19.1 or above). The number and percentage of subjects experiencing an AE will be summarized by the MedDRA System Organ Class (SOC) and Preferred Term (PT). AEs will be classified as pretreatment or treatment-emergent.

Pretreatment AEs are defined as AEs that were reported or worsened after signing the ICF up to the start of study drug dosing.

Treatment-emergent adverse events (TEAEs) for all cohorts except Cohort A7 are defined as AEs that started or worsened on or after the start of study drug dosing within the TE Period.

For Cohort A7, TEAEs will be assigned to each Treatment Group based on the start date of the AE and the start of study drug administration dates within the corresponding TE Period.

AE summary tables will be presented for TEAEs only and will include the following: (1) all TEAEs; (2) related (defined as possibly related, related, or unknown) TEAEs; (3) serious TEAEs; (4) TEAEs by severity; (5) TEAEs by relationship; and (6) TEAEs leading to treatment discontinuation. Summaries will be presented by MedDRA SOC and PT using frequency counts and percentages by Treatment Group and overall for each part. A subject with multiple occurrences of the same TEAE or a continuing TEAE will be counted only once under the highest reported severity and relationship. In addition, a listing containing individual subject AEs leading to death, SAEs, dose interruption, and permanent discontinuation will be listed separately. All AEs will be presented in individual subject data listings.

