12.3.5.1 Adverse Events

12.3.5.1.1 Parts A, B, and C

AEs will be coded according to MedDRA. The number and percentage of subjects experiencing an AE will be summarized by the MedDRA System Organ Class and Preferred Term. AEs will be classified as pretreatment or treatment-emergent.

Pretreatment AEs are defined as AEs that were reported or worsened after signing the ICF up to the start of study drug dosing.

Treatment-emergent AEs are defined as AEs that were reported or worsened on or after the start of study drug dosing through the Safety Follow-up Visit.

Only TEAEs will be summarized in tables. All summaries of TEAEs will be presented by the severity of the AE and relationship to the study drug. Some rules that will apply to the summarization of AEs are (1) a subject with multiple occurrences of the same AE or a continuing AE will be counted only once; (2) only the maximum severity level will be presented in the severity summary; and (3) only the worst relationship level will be presented in the relationship summary.

AEs leading to death, SAEs, dose interruption, and permanent discontinuation will be listed separately. All AEs through the Safety Follow-up Visit will be listed in an individual subject data listing, including pretreatment AEs.

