13.1.1.3 Documentation of Adverse Events

All AEs will be collected from the time ICF is signed until the following time points:

- For subjects who do not enroll: until time of screen failure (e.g., screen failure, withdrawal of consent)
- For enrolled subjects who have a Safety Follow-up Visit: through the Safety Follow-up Visit
- For enrolled subjects in Parts A, B, and C who do not have a Safety Follow-up Visit, 10 days after the last dose of study drug
- For enrolled subjects in Parts D, E, and F who do not have a Safety Follow-up Visit, the earliest of
 - o 28 days after the last dose of study drug, or
 - o the ETT Visit, if that visit is 3 weeks or later following the last dose of study drug (see [Section 9.1.2.7](#))

All subjects will be queried, using nonleading questions, about the occurrence of AEs at each study visit. When possible, a constellation of signs and/or symptoms will be identified as 1 overall event or diagnosis. All AEs for enrolled subjects will be recorded in the CRF and source document. AEs for subjects who are screened but not subsequently enrolled in the study will be recorded only in the subject's source documents. The following data will be documented for each AE:

- Description of the event
- Classification of “serious” or “nonserious”
- Date of first occurrence and date of resolution (if applicable)
- Severity
- Causal relationship to study drug(s)
- Action taken
- Outcome
- Concomitant medication or other treatment given

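### In Cohort A7 the SAP assigns adverse events to treatments by start date and omits worsening, so an event that worsens after a later dose may be tabulated under the earlier treatment

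*SAP*

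**What the plan says.** Protocol 12.3.5.1.1 gives one definition for Parts A, B and C, with no exception for A7: "Treatment-emergent AEs are defined as AEs that were reported or worsened on or after the start of study drug dosing through the Safety Follow-up Visit".

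SAP (Parts A, B and C) 9.3.1 narrows this. Outside A7, treatment-emergent events "are defined as AEs that started or worsened on or after the start of study drug dosing within the TE Period" (TE stands for treatment-emergent). The sentence for A7 contains no definition, only a rule, applied by TE period, for placing events: "TEAEs will be assigned to each Treatment Group based on the start date of the AE and the start of study drug administration dates". SAP 9.1 gives A7 three TE periods, one per treatment: fasted tablet from the Day 1 dose to the Day 7 dose, fed tablet from Day 7 to Day 13, and IV from Day 13 to the Safety Follow-up Visit.

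A further rule in 9.3.1 governs counting: "A subject with multiple occurrences of the same TEAE or a continuing TEAE will be counted only once under the highest reported severity and relationship". It does not confine the highest grade to the period in which that grade was reached.

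**The concern.** A7 is the only cohort in Parts A, B and C in which a subject passes through several treatments. It is therefore the only one where the question is not just whether an event is treatment-emergent but which treatment it belongs to. It is also the cohort for which the SAP leaves worsening out.

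Read literally, the start-date rule and the count-once rule together keep a continuing event with the treatment under which it began, and carry its later, higher grade back to that treatment. An event cannot worsen before it starts and the dosing order is fixed. Any misplacement therefore runs towards an earlier treatment, or out of the treatment columns altogether. SAP 9.3 names safety as the primary objective and lists the incidence of treatment-emergent events first among the safety endpoints. The A7 tables should therefore follow the protocol definition.

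**Working it through.** The plan gives no figure to reproduce, since the safety analysis is descriptive. The check applies the written rules to four invented event histories and compares them with a started-or-worsened rule applied within each period.

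Inputs: dosing on Days 1, 7 and 13 (Protocol Table 3-3; SAP 9.1); placement by start date and counting once at the highest grade (SAP 9.3.1); 8 subjects (SAP Table 6-1). Each history is assumed to be held as a single record whose start date is its first onset.

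| Invented history | SAP 9.3.1 as written | Started or worsened, by period |
|---|---|---|
| Mild Day 5, severe Day 8 | Fasted: severe. Fed: none | Fasted: mild. Fed: severe |
| Mild Day 10, severe Day 14 | Fed: severe. IV: none | Fed: mild. IV: severe |
| Mild Day 5, severe Day 14 | Fasted: severe. IV: none | Fasted: mild. IV: severe |
| Mild Day -1, severe Day 3 | No A7 column | Fasted: severe |

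Size: if all 8 subjects receive each treatment, one affected subject changes a column's entry by 1/8 = 12.5 percentage points. In the first three rows, 12.5 points of severe-event incidence sit under the earlier treatment instead of the later one. In the fourth row they are missing from every column.

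The single-record assumption decides the result. If a worsening is instead entered as a new record dated when it occurred, the start-date rule puts the worse grade in the later period, and the first three rows give the same answer under both rules. In the fourth row the new record would start on Day 3 and fall under fasted tablet. The documents on this assumption are as follows:

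- Protocol 13.1.1.1 includes in the adverse-event definition a condition already present that gets worse after consent. This may allow a worsening to be its own event, but it does not say that an on-study event already being followed gets a new record.
- Protocol 13.1.1.3 lists the date of first occurrence, the date of resolution and severity among the items documented for each event. It lists no date of worsening.
- Protocol 11.7.1 leaves completion of the adverse-event form to a separate guideline that is not among the documents.
- SAP 9.3.1 itself speaks of a continuing event having a highest reported severity, which fits single records but does not prove them.

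Two other places show that the sponsor can handle multiple periods. SAP 9.2.3 lets a concomitant medication in A7 count in more than one TE period. The SAP for Parts D, E and F (8.4.1) defines treatment-emergent events separately for the Run-in and Treatment Periods of Part E, and includes worsening in each.

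**The case against.** The strongest reply is that the misplacement is not established. Protocol 13.1.1.1 can be read to make a worsening an adverse event in its own right, and the form guideline and the A7 case report form, which would settle the matter, are not available. This stands, and it makes the effect conditional. It does not remove the gap, because nothing in the plan states the recording convention on which the A7 rule would depend.

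A second reply is that a highest grade per period cannot be derived from the fields in Protocol 13.1.1.3 if records are not split, so the repair would need data that may not exist. This stands in part. The per-period grade can be derived only where worsening is dated. But the SAP already needs to recognise worsening in every other cohort, and A7 can use the same derivation.

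Third, the impact is slight: 8 open-label subjects, one fixed sequence, no placebo and no testing. All events appear in listings, and serious events and those leading to death, interruption or discontinuation are listed separately. This stands in full.

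A reader might infer three stronger things that the documents do not support:

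- **That later worsening is always charged to the earlier treatment.** This fails if each worsening opens a new record.
- **That the rule biases a comparison of fasted tablet, fed tablet and IV.** With a single sequence, treatment is fully confounded with order, so the A7 event columns cannot support such a comparison under any placement rule. The aims specific to A7 are food effect and absolute bioavailability, which are secondary and pharmacokinetic.
- **That an event beginning before Day 1 and worsening after dosing is not treatment-emergent at all.** The protocol definition still covers it, and the A7 sentence in the SAP presupposes events already classed as treatment-emergent. The gap is that no A7 column is named for it.

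**Conclusion.** The point holds as a departure of the SAP from the protocol definition, with a conditional and small effect. SAP 9.3.1 takes A7 out of the started-or-worsened definition and places its events by start date, while Protocol 12.3.5.1.1 includes worsening without exception.

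If an ongoing event keeps one record and its first start date, worsening after the Day 7 or Day 13 dose is shown under the earlier treatment at the highest grade, and an event that began before Day 1 and worsened after dosing gets no A7 column. If every worsening is a new dated record, the start-date rule places it correctly. The documents do not say which applies.

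The size is 12.5 percentage points per affected subject, assuming 8 subjects per treatment. How many such events would occur is unknown. Only descriptive tables are affected, and no event is lost from the listings. This is a wording correction worth making, not a flaw in the study's main safety conclusions.

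**What to change.** In SAP (Parts A, B and C) 9.3.1, state that in Cohort A7 an event is treatment-emergent for each TE period in which it started or worsened, with worsening identified in the same way as for the other cohorts. Assign the worsened grade to the period in which the worsening occurred, and apply the count-once rule within each period. This also gives a column to an event that began before Day 1 and worsened after dosing.

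State the recording convention for worsening on the A7 case report form. Where worsening is not separately dated, say so, and flag in the listing any event that was ongoing across a dosing day.

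The cost is a few sentences and minor programming, with no new data collection. There are two drawbacks: one event may appear under two treatments, as medications already can, and the per-period grade will be available only where worsening is dated.
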